2 STUDY OBJECTIVES

2.1 **Primary Objective(s)**

- To evaluate the safety and tolerability of nalbuphine extended-release (NAL ER) tablets in the study population.
- To evaluate the effect of NAL ER tablets on the mean daytime cough frequency (coughs per hour) at Day 22 (dose 162 mg twice daily [BID]) as compared to placebo. Assessment is done using objective digital cough monitoring. Daytime is defined as the time the subject is awake in the 24 hours after the digital cough monitor is applied for use.

2.2 Secondary Objective(s)

- To evaluate the effect of NAL ER tablets on the mean relative change from baseline in 24hour (combined daytime and nighttime) cough frequency (coughs per hour) at Day 22 (dose: 162 mg BID).
- To evaluate the effect of NAL ER tablets on the mean relative change from baseline in nighttime cough frequency (coughs per hour) at Day 22 (dose: 162 mg BID).
- To evaluate the effect of escalating doses of NAL ER tablets on the mean change from baseline on the Evaluating Respiratory Symptoms (E-RS[™]) diary cough scale (E-RS diary question number 2) by treatment at Days 9, 16, and 22.
- To evaluate the effect of escalating doses of NAL ER tablets on the mean change from baseline in the Cough Severity Numerical Rating Scale by treatment at Days 8, 15, and 21.
- To evaluate the effect of escalating doses of NAL ER tablets on the mean change from baseline in the E-RS diary breathlessness scale (E-RS diary questions 7, 8, 9, 10, and 11) by treatment at Days 9, 16, and 22.
- To evaluate the effect of escalating doses of NAL ER tablets on the mean change from baseline in the 14-item the EXAcerbation of Chronic pulmonary disease Tool (EXACT[®]) version 1.1 e-diary tool total score by treatment at Days 9, 16, and 22.

- To evaluate the effect of escalating doses of NAL ER tablets on the mean change from baseline in the Patient Reported Outcomes Measurement Information System (PROMIS[®]) Item Bank v1.0 Fatigue Short Form 7a scale by treatment at Day 21.
- To evaluate the change in the Clinical Global Impression of Change (CGI-C) over time by treatment measured at Day 21.

3 INVESTIGATIONAL PLAN

3.1 Overall Study Design and Plan

This is a double-blind, randomized, placebo-controlled, 2-treatment, 2-period crossover efficacy and safety study in IPF subjects with NAL ER tablets for the treatment of cough.

The study consists of 2 treatment periods of 3 weeks, each followed by a washout period of 2 weeks.

During Treatment Period 1, eligible subjects will be randomized (1:1) to one of the following treatment arms:

- Arm 1: Active NAL ER tablets followed by crossover Placebo tablets in Treatment Period 2
- Arm 2: Placebo tablets followed by crossover NAL ER tablets in Treatment Period 2

Following 3 weeks of dosing in Treatment Period 1, subjects will complete a 2-week washout period before entering Treatment Period 2. Subjects assigned to Arm 1 will receive placebo tablets and subjects assigned to Arm 2 will receive NAL ER tablets during Treatment Period 2. A final 2-week washout period will occur at the completion of Treatment Period 2.

Subjects on NAL ER tablets will have the dose titrated from 27 mg once daily (QD) to 54 mg BID over a 5-day period and then maintained at 54 mg BID for approximately 4 days. Doses will be subsequently escalated and maintained at 108 mg BID over 1 week and then to 162 mg BID over 6 days.

Study visits will include screening to determine eligibility, and for each treatment period: visits at Day -1 for baseline assessments, at Days 8, 15, and 21 during treatment, and a follow-up at the end of the 2-week washout period. At study screening and the Day 21 visits during each treatment period, subjects will have blood drawn for safety analysis. Nalbuphine (and/or metabolites) plasma concentration will also be measured at Day 21. Subjects will complete questionnaires for efficacy evaluations and undergo safety evaluations including an ECG. At the baseline and Day 21 visits, during each treatment period, site staff will place an electronic cough monitor on the subject, which will be worn until the evening of the following day in order to obtain at least a full 24-hour recording period of cough frequency. At the end of each recording session, the monitor will be removed at home by the subject prior to bedtime. Subjects will complete a daily e-diary twice per day.

Subjects who discontinue investigational product, for reasons other than withdrawal of consent, will be considered to have prematurely discontinued treatment and will be asked to complete the premature discontinuation and 2-week off-treatment safety follow-up evaluations.

The schematic of the study design is provided in Figure 1.

The schedule of assessments is provided in Appendix 1 and Appendix 2.

Figure 1 – Study Schematic

3.2 Endpoints and Associated Variables

Primary Efficacy Endpoint

• Mean change in daytime cough frequency (coughs per hour) from baseline as assessed by objective digital cough monitoring at Day 22 by treatment. Daytime is defined as the time the subject is awake in the 24 hours after the digital cough monitor is applied for use.

Secondary Efficacy Endpoints

- Relative change in daytime cough frequency (coughs per hour) from baseline at Day 22 (dose: 162 mg BID) by treatment.
- Relative change in 24-hour (combined daytime and nighttime) cough frequency (coughs per hour) from baseline at Day 22 (dose: 162 mg BID) by treatment.
- Relative change in nighttime cough frequency (coughs per hour) from baseline at Day 22 (dose: 162 mg BID) by treatment.
- Mean change in the E-RS diary cough subscale (E-RS diary question number 2) from baseline, at Days 9, 16, and 22 by treatment.
- Mean change in the Cough Severity Numerical Rating Scale at Days 8, 15, and 21 by treatment.
- Mean change in the E-RS diary breathlessness subscale (E-RS diary questions 7, 8, 9, 10, and 11) from baseline at Days 9, 16, and 22 by treatment.
- Mean change in the 14-item EXACT v1.1 e-diary tool total score from baseline at Days 9, 16, and 22 by treatment.
- Mean change in the PROMIS Item Bank v1.0 Fatigue Short Form 7a scale from baseline at Day 21 by treatment.
- Mean change in the CGI-C over time measured at Day 21 by treatment.

| Trevi Therapeutics, Inc. | |
|--------------------------|---------------------------|
| TR12 | Statistical Analysis Plan |
| Safety | |

Safety will be assessed based on adverse events, clinical laboratory measurements, central cardiac core laboratory read ECGs, vital signs, spirometry and physical examinations.

Subjects will also complete the Subjective Opiate Withdrawal Scale (SOWS) on a daily basis via e-diary for 14 days following the last dose of investigational product, whenever that occurs and regardless of the reason (unless consent is withdrawn).

An independent Data Safety Monitoring Board (DSMB) will periodically review safety data.

Pharmacokinetics

Nalbuphine (and/or metabolites) plasma concentration will be measured.

3.2.1 Efficacy Variables

Cough frequency is recorder via a wearable digital cough monitor hookup (24-hour recording) provided by external vendor Vitalograph[®] hereby referred to as 'cough monitor'.

Baseline (pre-treatment) recording of cough frequency will be obtained at Visit 2 (day -1) for Treatment Period 1 and at Visit 6 (day -1) for Treatment Period 2. Period 1 baseline will be taken as the general study baseline as explained in the baseline definition at section 4.2.3 of this SAP.

Cough frequency will also be recorded at Visit 5 (day 21) for Treatment Period 1 and at Visit 9 (day 21) for Treatment Period 2.

Cough frequency will be captured in a 24-hour recording.

External vendor Vitalograph[®] will derive and provide daytime cough frequency at each pertinent visit.

3.2.1.1 Primary Efficacy Variable

Daytime cough frequency at Day 22 is the primary efficacy variable.

Hourly daytime cough frequency is derived by the external vendor and will be received as a transfer SAS dataset named 'FA' under variable FAORRES when FATEST='Cough average Score at daytime'.

"Daytime" is defined as the time the subject is awake in the 24 hours after the digital cough monitor is applied for use. Events, including sleep, late attachment and device removal, are identifiable in recording via combined assessment of cough monitor algorithms and specially trained cough analysts which will identify these periods from the waveform generated and by the content of the sounds heard. Vitalograph[®] analysts are trained in differentiating sleep periods from the subject being asleep. Consequently, identification of the possible sleep time is done by Vitalograph[®] analysts and will be indicated in the data transfer as date and time of sleep start and end.

Of note:

- If the patient gets up for a short period in the night i.e. use the bathroom or drink a glass of water, this will be counted as sleep time.
- If the patient gets up for a longer period, this will be classed as awake time.
- If two or more periods of sleep exist in a recording the start and end times of each sleep period will be identified.

Statistical Analysis Plan

The following events will be recorded and collected in the data transfer, together with start and end date as appropriate:

| Event Name | Description |
|-----------------------|--|
| Sleep | Sleep Period |
| Device Not Attached | The recording is on, but the device is not attached to the subject |
| Recording Ended Early | Recording duration is shorter than what was expected |
| Flagged Area | An area/period of the recording where there is an issue with the result that this period cannot be analyzed. |

Table 1 – Cough Monitor Events

The Vitalograph[®] data transfer will hold the daytime average coughs per hour based on the following calculation, rounded to two decimal places:

Daytime cough frequency = ((total cough events for a session not within Sleep, Device Not Attached, Recording Ended Early, Flagged Area event periods) / (recording length in seconds - Sleep, Device Not Attached, Flagged Area event period durations)) x 3600. A session is defined as that 24-hour period when cough recording is taking place for an individual subject. For a session with 'Recording Ended Early', the recording early end datetime will be the end datetime for the session. No events will be collected after the recording early end datetime.

Recording of daytime cough frequency is expected in treatment period 1 at Visit 2 (Study baseline: starting on day -1 and ending at day 1 prior to first IMP intake) and Visit 5 (starting on day 21 and ending on day 22), and in treatment period 2 at Visit 6 (Baseline: starting on day -1 and ending at day 1 prior to first IMP intake) and Visit 9 (starting on day 21 and ending on day 22).

A 24-hour recording is required per protocol at each appropriate visit. All recordings considered valid per Vitalograph[®] quality assessment will be used in analysis, irrespective of actual duration. Cough frequency will be computed based on the actual recording duration.

For the primary endpoint analysis, daytime cough frequency will be log transformed on the natural log scale; ratios will be then calculated per subject per period as log (Visit cough / Study baseline cough) which would represent, upon back transformation and subtraction from 100%, a percent reduction in daytime cough frequency versus study baseline.

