6 INVESTIGATIONAL PLAN

6.1 Study Design

This is a double-blind, randomized, placebo-controlled, 2-treatment, 2-period crossover efficacy and safety study in IPF subjects with NAL ER tablets for the treatment of cough. The study consists of 2 treatment periods of 3 weeks, each followed by a washout period of 2 weeks.

Treatment Period 1:

During Treatment Period 1, eligible subjects will be randomized (1:1) to one of the following treatment arms:

- Arm 1: Active NAL ER tablets followed by crossover Placebo tablets in Treatment Period 2
- Arm 2: Placebo tablets followed by crossover NAL ER tablets in Treatment Period 2

Following 3 weeks of dosing in Treatment Period 1, subjects will complete a 2-week washout period before entering Treatment Period 2. Subjects assigned to Arm 1 will receive placebo tablets and subjects assigned to Arm 2 will receive NAL ER tablets during Treatment Period 2. A final 2-week washout period will occur at the completion of Treatment Period 2.

NAL ER Dosing

Subjects on NAL ER tablets will have the dose titrated from 27 mg once daily (QD) to 54 mg BID over a 5-day period and then maintained at 54 mg BID for approximately 4 days. Doses will be subsequently escalated and maintained at 108 mg BID over 1 week and then to 162 mg BID over 6 days.

Study Visits:

Study visits will include screening to determine eligibility, and for each treatment period: visits at Day -1 for baseline assessments, at Days 8, 15, and 21 during treatment, and a follow-up at the end of the 2-week washout period. At study screening and the Day 21 visits, during each treatment period, subjects will have blood drawn for safety analysis. Pharmacokinetic (PK) analysis of nalbuphine plasma concentration will also be done at Day 21. Subjects will complete questionnaires for efficacy evaluations and undergo safety evaluations including an ECG. At the baseline and Day 21 visits, during each treatment period, site staff will place an electronic cough monitor on the subject, which will be worn until the evening of the following day in order to obtain at least a full 24-hour recording period of cough frequency. At the end of each recording session, the monitor will be removed at home by the subject prior to bedtime. Subjects will complete a daily e-diary twice per day.

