3.2.1.2 Secondary Efficacy Variables

3.2.1.2.1 24-hour cough frequency

24-hour cough frequency is defined as the total number of cough events recorded in a 24-hour period, divided by 24, rounded to the nearest 2 decimal places.

24-hour cough frequency per hour will be directly provided by Vitalograph® in the data transfer; this will be available in FA dataset under variable FAORRES when FATEST = 'Full Average Hourly Cough'.

The Vitalograph[®] data transfer will hold the 24-hour cough frequency average per hour based on the following calculation, rounded to two decimal places:

24-hour cough frequency = (total cough events for a session) / (recording length in seconds - Recording Ended Early, Device Not Attached, Flagged Area event period durations)) x 3600. A session is defined as that 24 hour period minus quality event periods when cough recording is taking place for an individual subject. For a session with 'Recording Ended Early', the recording early end datetime will be the end datetime for the session. No events will be collected after the recording early end datetime.

Of note: will be blank in the vendor file if the session is rejected.

For 24-hour cough frequency endpoint, a natural log transformation will be applied as described for daytime cough frequency in section 3.2.1.1.

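### A valid cough recording with no usable sleep time enters the secondary analysis as a 24-hour rate although it is an awake rate, and the SAP defines that rate in two conflicting ways

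*SAP*

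**What the plan says.** Protocol 6.1 has the monitor worn until the evening after the visit "in order to obtain at least a full 24-hour recording period of cough frequency". SAP 3.2.1.1 repeats the requirement: "A 24-hour recording is required per protocol at each appropriate visit". It then uses all recordings that pass the vendor's "quality assessment will be used in analysis, irrespective of actual duration. Cough frequency will be computed based on the actual recording duration".

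Short recordings are foreseen. Table 1 of the SAP lists an event for a recording that ended early, described as "Recording duration is shorter than what was expected", and for such a session "the recording early end datetime will be the end datetime for the session". Other events mark time when the device was not attached or the sound could not be analysed.

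SAP 3.2.1.2.1 gives two definitions of the secondary 24-hour rate. In words: "24-hour cough frequency is defined as the total number of cough events recorded in a 24-hour period, divided by 24". As the vendor's formula: total coughs in the session over "recording length in seconds - Recording Ended Early, Device Not Attached, Flagged Area event period durations", scaled to an hour. The only screen on a recording is vendor rejection, after which the value "will be blank in the vendor file if the session is rejected". Neither document gives the rejection criteria, a minimum number of awake hours, or a requirement that sleep be covered.

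SAP 4.11.3.1 analyses the log 24-hour rate with the same mixed model as the primary endpoint, so this secondary endpoint is formally compared between treatments. That model (SAP 4.11.2) takes one unweighted log ratio per subject and period.

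**The concern.** A 24-hour rate is a mixture of awake and asleep coughing. Protocol 11.1 itself describes night as a time of lower coughing. When the recorded time contains no sleep, the vendor formula has nothing to average down the awake rate, so it returns the awake rate unchanged. This can happen because recording stopped before sleep, or because the sleep hours were lost as unattached or unusable time. The night-time rate (SAP 3.2.1.2.2) cannot be computed for such a session, yet the session stays in the 24-hour analysis and may be compared with a full-day recording from the same patient's other period.

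The definition in words pushes the other way: dividing by 24 when fewer hours were usable counts the missing hours as cough-free. Two programmers following the same section could report different values.

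For the daytime endpoint a short recording still estimates coughs per awake hour, but from fewer hours, and the model gives it the same weight as a full day.

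**Working it through.** **The plan's own figure.** Protocol 11.1 gives 44 completers, a 40% reduction, a CV of 1.00 and two-sided 5%, and claims at least 80% power. On the log scale, δ = ln 0.60 = −0.511, σ = √ln(1 + 1²) = √0.693 = 0.833, and SE = 0.833 × √(2/44) = 0.178. Power is 82.1% (normal) or 80.3% (t, 42 df), so the claim reproduces. The documents give no figure for short recordings; what follows rests on stated assumptions.

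**24-hour rate with no recorded sleep.** Let the awake rate be 1, the sleep rate r, with 16 awake and 8 sleep hours. The true 24-hour rate is (16 + 8r)/24. The vendor formula returns 1. The overstatement factor is 24/(16 + 8r):

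| r | factor | overstatement |
|---|---|---|
| 0.05 | 24/16.4 = 1.463 | 46% |
| 0.10 | 24/16.8 = 1.429 | 43% |
| 0.20 | 24/17.6 = 1.364 | 36% |
| 0.30 | 24/18.4 = 1.304 | 30% |

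Wider assumptions give 14% (18 awake hours, r = 0.5: 24/21 = 1.143) to 71% (14 awake hours, r = 0: 24/14 = 1.714).

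**The two definitions compared.** Take 8 recorded awake hours and nothing else. The formula gives 8/8 = 1.00 times the awake rate. Dividing by 24 gives 8/24 = 0.33. The true value at r = 0.1 is 16.8/24 = 0.70. One definition overstates, the other understates.

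**Effect on the 24-hour treatment contrast.** If a share f of placebo recordings lacks the night and no active recordings do, the treatment ratio is multiplied by ((16 + 8r)/24)^f. At r = 0.1:
- f = 10%: 0.70^0.1 = 0.965, a spurious reduction of 3.5%.
- f = 20%: 0.70^0.2 = 0.931, a spurious reduction of 6.9%.

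If the share and the factor are equal under both treatments, the shifts cancel and only noise remains. At f = 10% the added log variance per recording is 0.10 × 0.90 × (ln 1.429)² = 0.09 × 0.127 = 0.011.

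**Effect on the primary endpoint.** Assume independent hours with hour-level CV c, so a log rate from h awake hours has sampling variance c²/h. A 3-hour recording then has 16/3 = 5.3 times the sampling variance of a 16-hour one. If 20% of on-treatment recordings last 3 rather than 16 awake hours, the added variance is 0.20 × (c²/3 − c²/16):
- c = 0.5: 0.0135, power (t) 79.5%.
- c = 1.0: 0.0542, power 77.3%.
- c = 1.5: 0.1219, power 73.7%.

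The comparison is with 80.3%. A short baseline recording matters less: both periods use the study baseline, so it cancels in the within-subject contrast for patients with both periods.

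**The case against.** The strongest reply is that the SAP does not accept every length. Vendor quality review comes before analysis and rejected sessions are blank, so the shortest recordings may never reach the model. This stands as a limit on frequency, not as a remedy: the criteria are not given, and nothing says that sleep must be covered.

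A reader might infer that an early stop leaves only the afternoon of the visit. The documents do not support that. No clinic time is given, Protocol 8.2.1 allows up to 36 hours of recording, and a recording that ended at 20 hours would count as ended early yet normally include the night.

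A reader might also set the log error of one no-night recording (ln 1.304 = 0.27 to ln 1.463 = 0.38) against the planned effect of 0.51. That comparison is not valid: the first concerns a single recording of the 24-hour rate, the second is a mean effect on the daytime rate.

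Safeguards exist. SAP 4.4.2 sends all deviations to a blinded review and plans analyses including and excluding data affected by major ones. The negative binomial sensitivity model brings in daytime duration. Both are incomplete. No recording-length criterion is named, and repetition on the per-protocol set is optional (SAP 4.5). The negative binomial model covers only the daytime endpoint, and its text calls duration an offset while its code enters it as a covariate.

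Finally, keeping all valid recordings in the primary analysis is defensible, since dropping short ones could remove data for treatment-related reasons. That stands, and the fix respects it.

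**Conclusion.** The firm defect is in the secondary 24-hour endpoint. By the SAP's own formula, a valid session without usable sleep time is an awake rate analysed as a 24-hour rate, and the definition in words contradicts that formula whenever usable time is not 24 hours. The overstatement is 30% to 46% for an affected recording, assuming 16 awake hours and a sleep/awake ratio of 0.05 to 0.30; the documents say only that night coughing is lower.

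It would go too far to say that the 24-hour treatment effect is biased. That needs an imbalance between treatments, for which the documents give no evidence. Even with 10% of placebo recordings affected and no active ones, the shift is about 3.5% at a ratio of 0.1. It would also go too far to call the primary result biased. There the expected effect is a modest loss of precision, unless the captured hours are unrepresentative in a way that differs by treatment. How many recordings are affected cannot be judged from the documents.

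**What to change.** 1. In SAP 3.2.1.2.1, delete or reconcile the divided-by-24 wording so that one definition remains, and set the 24-hour rate to missing when the sleep period was not recorded. Recombining the recorded awake and sleep rates by recorded hours is not an alternative. With coughs C and hours H for awake (a) and sleep (s), ((Ca/Ha) × Ha + (Cs/Hs) × Hs)/(Ha + Hs) = (Ca + Cs)/(Ha + Hs). This is the existing formula, and the sleep rate is undefined when Hs = 0.
2. For the primary endpoint, keep the main analysis on all valid recordings. Add one sensitivity analysis limited to recordings above a minimum analysable awake time, with the threshold fixed at the blinded data review, and report recording length by treatment.

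The cost is a few sentences in the SAP, one additional run and one summary. A few 24-hour values become missing, and a few short recordings leave the sensitivity analysis. No new data are needed.

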3.2.1.2 Secondary Efficacy Variables

3.2.1.2.1 24-hour cough frequency

24-hour cough frequency is defined as the total number of cough events recorded in a 24-hour period, divided by 24, rounded to the nearest 2 decimal places.

24-hour cough frequency per hour will be directly provided by Vitalograph® in the data transfer; this will be available in FA dataset under variable FAORRES when FATEST = 'Full Average Hourly Cough'.

The Vitalograph[®] data transfer will hold the 24-hour cough frequency average per hour based on the following calculation, rounded to two decimal places:

24-hour cough frequency = (total cough events for a session) / (recording length in seconds - Recording Ended Early, Device Not Attached, Flagged Area event period durations)) x 3600. A session is defined as that 24 hour period minus quality event periods when cough recording is taking place for an individual subject. For a session with 'Recording Ended Early', the recording early end datetime will be the end datetime for the session. No events will be collected after the recording early end datetime.

Of note: will be blank in the vendor file if the session is rejected.

For 24-hour cough frequency endpoint, a natural log transformation will be applied as described for daytime cough frequency in section 3.2.1.1.

